[name] currently is an undergraduate student in the Pre-Med program at Clemson University. The primary responsibilities of the undergraduate research assistants are to assist with data collection, assist with team meetings, prep manuscripts, coordinator with dyads and research personnel for implementation, manage incentive distributions, assist with PAC meetings, monitor headset cleaning practices, troubleshoot VR issues, and gain experience working with ID research teams.

[name]

[name] currently is an undergraduate student in the School of Nursing at Clemson University. The primary responsibilities of the undergraduate research assistants are to assist with data collection, assist with team meetings, prep manuscripts, coordinator with dyads and research personnel for implementation, manage incentive distributions, assist with PAC meetings, monitor headset cleaning practices, troubleshoot VR issues, and gain experience working with ID research teams.

The study will require purchasing a tablet device to set up the synchronized tandem experience within Tandem VR, connecting to the PICO Neo 3 HMDs. We have allocated \$2000 to fund purchasing of a tablet device with Network Attached Storage (NAS) allowing dyads to view the synchronized tandem experience through the Prisma Health Seed Grant. We have allotted \$850 for the NVIVO qualitative software and Otter software for qualitative transcription. Approximately \$400 has been allotted to fund four lunches for Research Recruiters for assisting with the recruitment of dyads, training on the intervention, and implementation of the Tandem VR intervention for the study. Funding of \$520 has been allotted to provide \$20 to the patient-caregiver dyads (\$10 gift cards for each) for participation in the study. Approximately \$1200 has been allotted for the Patient Advisory Council to meet with researchers to discuss the experience within Tandem VR (\$50 to each member of the patient dyad participating).

C. PROPOSED INTERVENTION

1. Treatment

The Tandem VR intervention will include immersive, 360-degree audio-visual experiences of available Upstate SC nature scenes using Pico Neo 3 HMDs (Figure 1).

These experiences will be personalized to each dyad using a novel software system developed during this project. The system contains seamless, pre-loaded, and customized, virtual reality experiences of the patient’s choosing as the patient elected earlier on their VR intake form during consent. VR experiences from around the world and an estimated 50+ nature-based locations in the Upstate will be available to patients and caregivers to choose from. Dyads will indicate which locations elicit positive memorable experiences and in what order these locations should be presented, to create a cohesive storyline. The software is expected to then form a single video file that will transfer to each HMD via the cloud for playback during the Tandem VR experience. These individual videos will range from 5 to 15 minutes and include well-known forested areas, rivers, ponds, and parks. Personalized audio is expected to be available for each location as well and include a large selection of mix-and-made restorative nature sounds such as water flowing, wind, and bird songs.¹⁷ Dyads will engage with the intervention at least one time through the assistance of training hospice team members.

2. Devices

Pico Neo 3 is an all-in-one VR system but will be used in tandem with a tablet device to allow for synchronized viewing by patient-caregiver dyads through the HMDs. iPad device with Network Attached Storage (NAS) to connect HMDs in the synchronized experience. The Tandem VR nature-based content will be developed for this study.

D. POPULATION

Prisma Health Hospice of the Foothills patients with projected life expectancy of <6 months (established by hospice experts) and their informal caregivers. Study will be conducted in the home setting.

1. Inclusion Criteria

- Ability to speaking English
- Participants, patients and caregivers, must be at least 18 years old or older.
- Projected life expectancy of <6 months (established by Prisma Hospice Medical Directors and hospice staff)
- Cognitively intact (has sufficient judgment, planning, organization, self-control)

2. Exclusion Criteria

- Have cognitive impairment that affects protocol participation. This will be done with the assistance of Research Recruiters (social workers, other hospice personnel recruited for the study, and the research team members such as the Research Assistants, PIs and Co-Is) to assess eligibility.
- Have a condition that interferes with VR usage, including but not limited to seizures, facial injury precluding safe placement of headset.
- Have a prognosis of hours or actively dying at the time enrollment.
- Patients with motion sickness
- Patients with claustrophobia
- Patients with visual and hearing impairment
- Patients with inability to speak English.

3. Sample Size

n/a

4. Local Number of Participants

The study will recruit 20+ patient and caregiver dyads from Prisma Health Hospice of the Foothills

5. Study-Wide Number of Participants

This is a multi-site study, and we expect to recruit a total of 20+ patient-caregiver dyads from Prisma Health Hospice of the Foothills across the upstate of South Carolina through hospice and bereavement services in Oconee, Pickens, Greenville, and Anderson counties.

6. Recruitment Methods

Prisma Health Institutional Review Board approvals will be obtained for the study.

Participants will be primarily recruited using flyers and word-of-mouth. Research Recruiters (n=10) will be CITI trained, affiliated with, and working alongside with Prisma Health Hospice of the Foothills staff. Recruiters will assist with consenting dyads, launching the intervention, data collection, and offering expert insights on the use of the intervention as a non-pharmacological modality. Ongoing dialogue between the social workers and the research team will allow for continuous improvement in the intervention delivery and offer data on the acceptance of the intervention for hospice patients and caregivers. All information will be explained in a nontechnical fashion and ample time will be available for the participants to ask any questions. This study will recruit a total of 20+ patient-caregiver dyads who will then be screened using the inclusion and exclusion criterion to ensure participant eligibility.

Flyers about the study, word-of-mouth from Research Recruiters.

E. SPECIFICS OF STUDY PROCEDURES

Screening and Pre-intervention

- Enrolled participants will be consented to per approved Prisma Health consent.
- Consented participants will be screened by the research assistant to ensure eligibility of participants, based on inclusion/ exclusion criterion and will complete the Tandem VR Intake form.
- Eligible participants will meet with the Research Recruiters and baseline data will be collected including demographics. Also, participants will complete Wisconsin Brief Pain Questionnaire (WBQP), Collett-Lester Fear of Death (FOD) scale, and McGill Quality of Life (QOL) scale directly before and after the intervention.
- Research recruiters will meet with participants in the home setting to assist dyads and implement the Tandem VR intervention.
- Upon completion of the intervention, Research Recruiters will collect the Tandem VR equipment and readminister the WBQP, FOD, QOL instruments, and semi-structured interviews.
- Consent from dyads will have been obtained by the Research Recruiters to participate in the Patient Advisory Council (PAC) to work with the researchers on understanding the experience.

Intervention

All procedures completed below will be done on one home visit.

The Tandem VR intervention will be carried out in the patient-caregiver dyad's home setting with the Research Recruiters implementing the experience. Each member of the dyad will initially complete the McGill Quality of Life Questionnaire-E (MQOL-E), Wisconsin Brief Pain Questionnaire (BPQ), and Collet-Lester Fear of Death (FOD) Scale prior to beginning the Tandem VR experience through an electronic medium.

Following completion of the pre-intervention forms, the dyads will be assisted by the Research Recruiter to don the VR HMD. The Research Recruiter will ensure safety for both participants while using the devices. The Research Recruiter will then initiate the Tandem VR experience using the iPad device to synchronize the nature-based scene for viewing. The duration of the experience will be 5-15 minutes.

Upon completion of the Tandem VR intervention, the HMD devices will be removed from the dyad participants. They will then complete the three instruments of the MQOL-E, BPQ, and FOD. Following the completion of the post-intervention documents, the Research Recruiter will conduct the semi-structured interview with the participants. Each participant will be asked the following questions to reflect on their experience:

- Tell us about your experience in Tandem VR?
- What was it like being together in the Tandem VR experience?
- Was there anything about the Tandem VR experience that helped you?
- Was there anything about the Tandem VR experience you feel could be improved?
- Were there any unusual sensations such as dizziness, lightheadedness, or disorientation while you were in the Tandem VR experience? If so, please explain.

These procedures will be carried out with each dyad for a duration of 8-16 weeks to ensure enough participation in the study. Research Recruiters will also identify participant dyads that can participate in the PAC to discuss the experience with the primary research team.

At this point the study will be completed for the dyads.

The study will recruit 20+ patient-caregiver dyads from Prisma Health Hospice of the Foothills. The participants will be enrolled in the study for 1 intervention with Tandem VR. Each dyad will receive \$20 for participating in the study (a \$10 gift card to the patient and \$10 gift card to the caregiver).

Cleaning and Disinfection of VR -Head Mounted Display (VR- HMD)

As part of a clinical study, virtual reality headsets will need to be reused between patients. At the end of the intervention the VR- HMD will be disinfected. Infection control measures include:

- Hand hygiene will be performed prior to cleaning and disinfection of HMD.
- Headsets that are disinfected will be handled with clean hands to prevent contamination.
- Participants will be instructed to not use headsets if there is a break in their integrity or have visible soiling.

Cleaning of HMD:

Use manufacturer's approved (VRCOVER antibacterial wipes) wipes for removal of all visible bioburden from headset and controller for disinfection.

Disinfection of HMD:

Follow cleaning instructions using disinfection wipes.

The above cleaning protocol has been approved by Prisma Health Infection Prevention.

Participants will continue to follow-up as normal with their physicians at Prisma Health Hospice of the Foothills.

1. Study Timelines

Tandem VR: Synchronized Nature-Based Experiences in Virtual Reality for Hospice Patients and their Caregivers

Table 1 Schedule of Assessments (Study Calendar)

Procedures	Pre-Intervention	Post-Intervention	PAC Meeting (Week 8)
Informed consent	X		
Inclusion/exclusion criteria	X		
Demographics	X		
Cognitive Assessment	X		
McGill Quality of Life Questionnaire-E (MQOL-E)	X	X	
Wisconsin Brief Pain Questionnaire (BPQ)	X	X	
Collett-Lester Fear of Death (FOD) Scale	X	X	
Semi-Structure Questions		X	
Dyads for PAC			X

Timeline of Study

*N_{total} ≥ 20 Patient-Caregiver Dyads

Inclusion Criteria:

- Ability to speaking English
- Projected life expectancy of <6 months (required Hospice eligibility per Centers for Medicare/Medicaid)
- Cognitively intact (has sufficient judgment, planning, organization, self-control)

Exclusion Criteria:

- Have cognitive impairment that affects protocol participation. This will be done with the assistance of Research Recruiters (social workers, other hospice personnel recruited for the study, and the research team, such as the Research Assistants, PIs, and Co-Is) to assess eligibility.
- Have a condition that interferes with VR usage, including but not limited to seizures, facial injury precluding safe placement of headset.

- Have a prognosis of >6 months from the time enrollment.
- Have a prognosis of hours or actively dying at the time enrollment.
- Patients with motion sickness
- Patients with claustrophobia
- Patients with visual and hearing impairment
- Patients with inability to speak English.

****All patients in the dyad will continue their current standard of symptom management throughout the study of 8-16 weeks****

2. Study Endpoints

For each dyad, the study will end after 1 use of the intervention. Dyads will be recruited to participate in the PAC extending time for a period of 8 weeks where they will meet with researchers to discuss the experience. We anticipate the total duration of the study to be approximately 12 months following which all the compiled data will be analyzed and published.

3. Outcome Measures/Data

Primary outcomes

1. Well-being will be measured upon the patient's enrollment in the study and post-intervention with the McGill Quality of Life Questionnaire-E (MQOL-E).
This assesses eight important life domains: cognition, healthcare, environment, feeling like a burden, and their relationships with physical, psychological, social, and existential/spiritual domains. The 20-item questionnaire uses a 0-10 response scale and is used internationally by hospice teams to assess QOL.
2. Change in pain interference as assessed with the Wisconsin Brief Pain Questionnaire (BPQ) [Time Frame: Pre-Intervention(baseline), Post-intervention]
Pain will be assessed with the Brief Pain Inventory (BPI). Patients will rate their pain from 0=no pain to 10=worst pain imaginable in response to items such as "average pain," "worst pain" and "least pain" over the last 7 days and "pain right now". An average of the responses to these items is used to create a single pain severity score.
3. Change in perception of fear of death with the Collett-Lester Fear of Death Scale [Time Frame: Pre-Intervention(baseline), Post-intervention]
4. Open-ended questions will be asked to determine the perceived benefit and value of the Tandem VR post-intervention with patient-caregiver dyads.

Secondary Outcomes

Follow-up semi-structured interviews with the hospice team and Research Recruiters will provide valuable information about the likelihood of integrating this intervention as a treatment modality for future dyads.

4. Data Collection Methods and Instruments Used

In this study, demographic data will be collected from all the participants. Demographic data will include age, sex, and race which will be used for secondary data analysis. In addition, EPIC EMR chart review would be used to collect demographic data from all the participants. In addition, we will also collect the medical record number (MRN), type of diagnosis, and life expectancy. Patient reported outcomes (PROs) will be measured using standardized symptoms assessment tools per study protocol. Standardized symptom assessment tools used in this study will include:

- McGill Quality of Life Questionnaire-E (MQOL-E)
 - Wisconsin Brief Pain Questionnaire (BPQ)
 - Collett-Lester Fear of Death Scale
 - Tandem VR Interview Guide
 - Tandem VR Intake Form
-
- (McGill Quality of Life Questionnaire-E (MQOL-E)
http://www.npcrc.org/files/news/mcgill_quality_of_life.pdf

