The primary aim of this study is to measure the impact on QOL using Tandem VR with patient-caregiver dyads transitioning to EOL. Our study will utilize an approach where participants will be asked to wear a VR HMD presenting Tandem VR content in a home setting. In addition to measuring the improvement in QOL, this study seeks to assess the efficacy of Tandem VR on patient-caregiver reported outcomes including pain and fear of death and assess the acceptability and safe use of Tandem VR in a home setting. The study will recruit 20+ patients from Prisma Health Hospice of the Foothills, who will be enrolled for treatment with Tandem VR. Research Recruiters will assist eligible patient-caregiver dyads in using the Tandem VR intervention in the comfort of their own home. The objective is to gather data on patients transitioning to EOL after being exposed to Tandem VR. The study will collect patient-caregiver reported outcomes including QOL, pain, and fear of death. The investigators will also assess acceptability and safety of Tandem VR at home. The investigators will also collect qualitative data following participants' Tandem VR experience to better understand the dyads' preferences, thoughts, and feelings about the intervention. Qualitative data will be garnered through audio recording in Otter, direct observation, and an interview. Outcomes will be measured before, and after the intervention. We expect that this study will demonstrate Tandem VR is an effective

non-pharmacologic treatment for improving QOL at EOL in patient-caregiver dyads; moreover, we expect Tandem VR will be acceptable and safely deployed in home settings.

IV. DESIGN & METHODS

A. STUDY DESIGN

Mixed-methods interventional study design: The study will recruit 20+ patient-caregiver dyads from Prisma Health Hospice of the Foothills enrolled in home care or at the hospice house. Once recruited, the dyads will be screened using the inclusion and exclusion criterion to ensure study eligibility. Dyads will also be offered the opportunity to participate in the Patient Advisory Council (PAC) to add further details on the experience in Tandem VR.

B. SETTING

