The risks associated with participation in this study are no greater than those typically encountered in normal day activities. Certain aspects of the participant’s demographics will be collected for this study. Loss of privacy may lead to problems with insurability or social stigmatization. In terms of privacy, participant’s data and associated records will be kept in a secure encrypted, password-protected database. Confidentiality of participant information and study activities will also be emphasized to all research personnel. These risks are considered to be minimal and are addressed in the protocol and consent form.

Participants may develop VR-related symptoms such as motion sickness effect, nausea, and headache, often referred to as cybersickness. Measures will be taken to assess if any symptoms of cybersickness occur and discontinue the intervention immediately. The greatest risk is the possible release of your personal health information. The study records are considered confidential, but absolute confidentiality cannot be guaranteed. This study may result in presentations and publications, but steps will be taken to make sure patient data is deidentified. Some of the questions in the surveys/questionnaires are personal and may be upsetting to some participants. The study doctor or staff will be available to discuss these questions should you have a concern or problem. You do not have to answer any questions that you do not want to answer.

In case patients or patient caregivers become emotional during the Tandem VR experience, a Hospice care on-call social worker will be providing real-time and immediate counseling.

2. Potential Benefits to Participants

We expect that this study will demonstrate Tandem VR is an effective non-pharmacologic treatment for the management of physiological distress of patient-caregiver dyads; moreover, we expect Tandem VR will be feasibly and safely deployed in home settings. The expected outcomes from this study include reduction in pain, reduced fear of death and improved quality of life for participants. This intervention is also likely to show improved interactions between patient-caregiver dyads through the imagery used in Tandem VR. The outcomes from this study will be used

to optimize Tandem VR to user satisfaction. The results will also be used to inform and refine future design guidelines and practices for the implementation of Tandem VR for patient-caregiver dyads in the hospice home setting.

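### The only specified VR side-effect question does not name nausea or headache and stops at headset removal, so these harms may be under-reported

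*Protocol*

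**What the plan says.** The last of the five interview questions in Protocol IV.E (Intervention) is "Were there any unusual sensations such as dizziness, lightheadedness, or disorientation while you were in the Tandem VR experience", followed by "If so, please explain". The same question is repeated under IV.E.5 (Data Management, Qualitative Data).

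On timing, the headset is removed, the three outcome instruments are completed again, and then: "Following the completion of the post-intervention documents, the Research Recruiter will conduct the semi-structured interview with the participants". After the interview, "At this point the study will be completed for the dyads". In Table 1 the row "Semi-Structure Questions" is marked post-intervention only, and no row covers adverse events or cybersickness.

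Protocol V.A.1 (Risks to Participants) states: "Participants may develop VR-related symptoms such as motion sickness effect, nausea, and headache, often referred to as cybersickness". The next sentence adds: "Measures will be taken to assess if any symptoms of cybersickness occur and discontinue the intervention immediately".

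Safety is among the study's aims. Protocol III.B sets out to "assess the acceptability and safe use of Tandem VR in a home setting". Neither the outcome list in Protocol IV.E.3 nor the SAP contains a safety outcome. The SAP plans means and standard deviations for the three scales and themes for the open-ended answers.

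**The concern.** The question differs from the protocol's own risk statement in content and in time window.

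- **Content.** Nausea and headache are named as expected VR effects, but neither is put to the participant as one. Someone who often has nausea or headache may not think of either as an unusual sensation.
- **Window.** The wording looks back only at the time in the headset. A symptom that begins after removal, while the questionnaires are being completed and the recruiter is still present, lies outside it.
- **Baseline.** The question is asked once, afterwards. In people enrolled in hospice, a symptom reported then may have been present before the session.

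The protocol expects to conclude that the intervention can be used safely at home, and this question is the only specified prompt aimed at VR side effects. If it elicits the expected harms incompletely, a low count says little about safety.

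**Working it through.** The plan has no figure to reproduce: the Sample Size section is marked not applicable and no symptom rate is given. The check is a comparison of texts, followed by an illustration of scale.

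**1. Named harms against prompts**

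| Harm named in V.A.1 | Prompted in the interview question? |
|---|---|
| Motion sickness effect | Not by name; dizziness and disorientation can fairly be read as part of it |
| Nausea | No |
| Headache | No |

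The clear gap is nausea and headache.

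**2. Window against timing**

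The exposure lasts 5 to 15 minutes (IV.E). The recruitment script in IV.B.1 puts the intervention and interview at about 60 minutes. Taken at face value, 60 − 15 = 45 to 60 − 5 = 55 minutes lie outside the window. The documents do not say how much of that follows headset removal, but it includes all three repeated questionnaires.

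**3. Other places where a symptom could surface**

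- *Other interview questions* are open, so a symptom can be volunteered. None asks about symptoms.
- *Direct observation and audio recording* (III.B) and *field notes* (IV.E.5) may record visible distress. No symptom list is attached to them.
- *Pain scale*, repeated before and after, includes a current-pain item. As described in IV.E.3, four named ratings, three of them looking back over 7 days, are averaged into one score. If a new headache raised only the current-pain rating by 4 points (assumed), the average would rise by 4 / 4 = 1 point, with nothing to mark it as headache.
- *MQOL-E*, also repeated, is described as including a physical domain. Its items are not in the text, and nothing in the description links an answer to the headset.
- *The cybersickness assessment promised in V.A.1* has no instrument, time point, assessor or record, and is tied to stopping the session. It does not clearly reach symptoms that begin afterwards.

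**4. Scale (illustration only)**

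Input from the plan: at least 20 dyads, so n = 20 × 2 = 40 people. Assumptions: true symptom rate p, fraction of cases reported c, and independence between people, including within dyads.

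Expected reports = 40 × p × c. P(at least one report) = 1 − (1 − p × c)^40.

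| p | c = 1 | c = 0.5 | c = 0.25 |
|---|---|---|---|
| 5% | 2 (0.871) | 1 (0.637) | 0.5 (0.395) |
| 10% | 4 (0.985) | 2 (0.871) | 1 (0.637) |
| 20% | 8 (1.000) | 4 (0.985) | 2 (0.871) |

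Each cell gives expected reports, with P(at least one) in parentheses.

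If nobody reports the symptom, the one-sided 95% upper bound on the reported rate is 1 − 0.05^(1/40) = 7.2% (13.9% for 20 patients alone). This bounds the true rate only if c = 1. At c = 0.5 the bound on the true rate is 7.2% / 0.5 = 14.4%.

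**The case against.** The best defence is that symptoms have several routes into the data. The three sensations are offered as examples, so in-session nausea or headache can be reported under the same question. The follow-up invites explanation, and the other questions are open. The list of harms in V.A.1 is also illustrative, so a word-by-word comparison of the two lists proves little by itself. The recruiter is present, V.A.1 commits the study to assessing cybersickness, and IV.D.2 excludes patients with motion sickness. In a qualitative interview, asking openly rather than symptom by symptom is a legitimate choice. The interview guide's content is not in the text, so any further probes in it cannot be checked.

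Much of this stands, and it rules out some stronger readings. A reader might infer that the named harms will be missed; the documents support only that they may be. A reader might take this for the only symptom question; the pain scale and MQOL-E are repeated after the session, and Protocol IV.E.4 lists both as symptom assessment tools. A reader might count none of three harms covered; motion sickness is partly covered by the prompts.

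Two things remain. Treating the sensations as examples widens the content of the question but not its time window. And a promised assessment with no stated method cannot be relied on to fill either gap. The suggestion that habitual symptoms would not be seen as unusual is plausible, but no document shows it, and it applies less readily to caregivers.

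**Conclusion.** The point holds as a limited weakness in measurement. The only specified VR side-effect question omits nausea and headache, which the protocol itself lists as VR harms, and closes its window at headset removal. The other routes may catch some symptoms, but none asks about nausea or identifies headache as a VR effect. Under-reporting of these harms is possible, and after-removal effects have no defined prompt. This weakens the stated aim of assessing safe use at home.

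Its size is unknown: the table above rests on assumed rates and reporting fractions. A reader might also infer an overall bias towards a finding of safety. That is not shown, because without a baseline, symptoms already present could be reported as VR effects and push the other way. Nor does the plan set a safety threshold that this question would decide.

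**What to change.** Reword the question in Protocol IV.E (Intervention), in IV.E.5 and in the interview guide so that it names nausea, headache and motion sickness alongside the three existing sensations. Extend its window to *during the experience or since the headset came off*, and keep the invitation to explain.

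Ask the same items once before the headset goes on, and add the corresponding pre- and post-intervention entries to Table 1. Symptoms already present can then be told from new or worse ones. In a single-visit study without a control group this shows timing, not cause.

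The recruiter already present can do this in about a minute more per participant. Prompting by name may slightly raise the reported frequency, which should be acknowledged when results are presented. The change concerns measurement only and leaves the handling of symptoms as it is.

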### **Primary outcomes**

1. Well-being will be measured upon the patient's enrollment in the study and post-intervention with the McGill Quality of Life Questionnaire-E (MQOL-E).

This assesses eight important life domains: cognition, healthcare, environment, feeling like a burden, and their relationships with physical, psychological, social, and existential/spiritual domains. The 20-item questionnaire uses a 0-10 response scale and is used internationally by hospice teams to assess QOL.

2. Change in pain interference as assessed with the Wisconsin Brief Pain Questionnaire (BPQ) [ Time Frame: Pre-Intervention(baseline), Post-intervention]

Pain will be assessed with the Brief Pain Inventory (BPI). Patients will rate their pain from 0=no pain to 10=worst pain imaginable in response to items such as "average pain," "worst pain" and "least pain" over the last 7 days and "pain right now". An average of the responses to these items is used to create a single pain severity score.

3. Change in perception of fear of death with the Collett-Lester Fear of Death Scale [ Time Frame: Pre-Intervention(baseline), Post-intervention]

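### Primary outcome 2 names two pain instruments and two constructs, and its score as written would shrink any immediate change in pain

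*Protocol*

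**What the plan says.** Protocol IV.E.3 (Outcome Measures/Data) and the SAP (Primary outcomes, item 2) carry the same text for the second primary outcome:

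- The heading is "Change in pain interference as assessed with the Wisconsin Brief Pain Questionnaire (BPQ", with time frames before and after the intervention.
- The next sentence changes the instrument: "Pain will be assessed with the Brief Pain Inventory (BPI".
- The items are given as examples, each rated 0 to 10: "average pain,' 'worst pain' and 'least pain' over the last 7 days and 'pain right now".
- The scoring rule is "An average of the responses to these items is used to create a single pain severity score".

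On timing, Protocol IV.E (Specifics of Study Procedures) has the questionnaires completed "directly before and after the intervention". It adds "All procedures completed below will be done on one home visit" and "The duration of the experience will be 5-15 minutes". Section IV.E.2 ends the study for each dyad after one use.

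On analysis, Protocol IV.E.7 plans t-tests of outcomes and of symptom changes, with pain as the example. The SAP plans means and standard deviations for each of the three quantitative measures. Neither plans a separate result for current pain.

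**The concern.** There are two problems, and the first needs no assumption.

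First, one outcome definition holds two constructs (interference and severity) and two instruments (BPQ and BPI). The SAP repeats the text, so it does not settle the matter. Followed as written, a severity score would be reported under an interference label.

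Second, as the outcome text stands, most of the score describes the past week, while the two forms are separated by one short session. A 5-15 minute experience can do little to a truthful answer about the last 7 days. The one named item that asks about the present is averaged with three that do not. The published mean change would then be a fraction of whatever happened to current pain, and a reader could take it at face value.

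**Working it through.** **Step 1. Construct and instrument, place by place.**

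- Outcome heading (Protocol IV.E.3 and SAP): interference, BPQ.
- Outcome text (same places): BPI, severity average.
- Procedures (Protocol IV.E): Wisconsin questionnaire only, under two different abbreviations.
- Table 1, IV.E.4 and IV.E.5: "Wisconsin Brief Pain Questionnaire (BPQ" only, with no BPI entry.
- Aims and objectives (II.B, III.A, III.B) and expected benefits (V.A.2): pain, without the word interference.

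The BPI is therefore the outlier on instrument, and interference is the outlier on construct. No visible text lists interference items or an interference score. The content of the appended BPQ form is not in the text reviewed, so its items and recall periods could not be checked.

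**Step 2. Session against recall window.** Seven days are 7 × 24 × 60 = 10,080 minutes. The session is 5/10,080 = 0.05% to 15/10,080 = 0.15% of that window.

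**Step 3. How much of a change in current pain reaches the score.** The documents give no figure to reproduce, so this is conditional arithmetic. Assumptions: exactly the four named items, equal weights, and literal recall, with worst and average pain over 7 days treated as fixed. For average pain this is close: even a 2-point fall lasting 15 minutes moves a 7-day average by 2 × 15/10,080 = 0.003 points.

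Let N be current pain before the session, L the 7-day least pain before it (L ≤ N), and D the fall in current pain. Least pain falls only if the session produces a new 7-day low, that is, by max(0, L − (N − D)). So:

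fall in composite = [D + max(0, L − (N − D))] / 4

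- Lower end: L is already at or below N − D. The composite falls by D/4. Example with assumed N = 5, L = 2, D = 2: (2 + 0)/4 = 0.5.
- Upper end: L = N. Least pain falls by the full D and the composite by D/2. Example with assumed N = L = 5, D = 2: (2 + 2)/4 = 1.0.

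**Step 4. Sensitivity.**

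- The item list is introduced as examples. If there were five or six items, the extra ones also 7-day and fixed, the range would be D/5 to 2D/5 (20-40%) or D/6 to 2D/6 (17-33%). Extra items about current pain would dilute less.
- If recall is not literal and each of the three 7-day items moves by a fraction f of D, the share shown is (1 + 3f)/4: 25% at f = 0, 43.75% at f = 0.25, 62.5% at f = 0.5 and 100% at f = 1. Beyond a true new low in least pain, that movement would be retest noise or recall bias, not relief over the past 7 days.

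**The case against.** The strongest objection is that the 7-day items and the averaging rule appear only in the text that follows the BPI sentence, which Step 1 identifies as the outlier. If the BPQ is the form handed out, its recall periods may differ. This stands, and it makes the recall point conditional on the outcome text. It does not help the definition: the outcome would then be described by items from a form that is not given.

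A reader might go further and infer that the composite could not be told apart from no change, or that the study loses power. The documents do not support either reading. In the Step 3 model, when current pain falls, the composite always falls too. If least pain stays fixed for everyone, the mean and the standard deviation of the change are both divided by 4, so a test on the change is unaffected. Power would fall only if the 7-day ratings added noise, and the documents give no standard deviations from which to judge that.

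A reader might also apply the 30-50% pain reduction cited in Protocol II.A as a benchmark. The documents do not say which pain measure that study used, so it is not used here.

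Two further points stand in part. A single item is less reliable than a multi-item score, which argues for reporting both rather than replacing one with the other. Protocol IV.E.5 keeps raw item-level data where applicable, so current pain might be recovered later, but that analysis would be unplanned.

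**Conclusion.** The contradiction is plain on the page: primary outcome 2 has an interference heading on the BPQ, names the BPI in its text, and defines only a severity score. This should be fixed before analysis.

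The recall mismatch holds as the outcome text is written. With four items, equal weights and literal recall, only a quarter to a half of a fall in current pain reaches the composite, so the reported mean change would understate immediate relief. The size rests on those assumptions and on a form that could not be checked. The harm is a mislabelled and understated result. No loss of power or of information is claimed.

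**What to change.** - **Protocol IV.E.3 and SAP item 2:** name one instrument and one construct, and make the heading match the score. Which to keep is the sponsor's choice. If interference is intended, state its items, recall period and score.
- **Protocol IV.E.3 and IV.E.7, SAP item 2 and the SAP sentence on means and standard deviations:** pre-specify the change in *pain right now* (0-10), from directly before to directly after the session, as the measure of immediate pain change, reported alongside the composite.
- **Before doing so:** confirm that the administered form contains that item.

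The cost is wording in four places and one more reported result. No new data are needed if the form already has the item. The single item's lower reliability is the reason to report both results.
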